5.4.2 Reporting Requirements for Serious Adverse Events and Adverse Events of Special Interest

5.4.2.1 Events That Occur prior to Study Drug Initiation

After informed consent has been obtained but prior to initiation of study drug, only serious adverse events caused by a protocol-mandated intervention should be reported. The paper Clinical Trial Serious Adverse Event/Adverse Event of Special Interest Reporting Form provided to investigators should be completed and submitted to the Sponsor or its designee immediately (i.e., no more than 24 hours after learning of the event), either by faxing or by scanning and emailing the form using the fax number or email address provided to investigators.

5.4.2.2 Events That Occur after Study Drug Initiation

After initiation of study drug, serious adverse events and adverse events of special interest will be reported until 5 months after the final dose of study drug *or until the EoT for ETT Week 101 visit (whichever is longer)*. Investigators should record all case details that can be gathered immediately (i.e., within 24 hours after learning of the event) on the Adverse Event eCRF and submit the report via the electronic data capture (EDC) system. A report will be generated and sent to Roche Safety Risk Management by the EDC system.

In the event that the EDC system is unavailable, the paper Clinical Trial Serious Adverse Event/Adverse Event of Special Interest Reporting Form provided to investigators should be completed and submitted to the Sponsor or its designee immediately (i.e., no more than 24 hours after learning of the event), either by faxing or by scanning and emailing the form using the fax number or email address provided to investigators. Once the EDC system is available, all information will need to be entered and submitted via the EDC system.

Instructions for reporting serious adverse events that occur >5 months after the final dose of study treatment are provided in Section 5.6.

5.4.3 Reporting Requirements for Pregnancies

5.4.3.1 Pregnancies in Female Patients

Female patients of childbearing potential will be instructed to immediately inform the investigator if they become pregnant during the study or within 5 months after the final dose of study drug. A paper Clinical Trial Pregnancy Reporting Form should be completed and submitted to the Sponsor or its designee immediately (i.e., no more than 24 hours after learning of the pregnancy), either by faxing or by scanning and emailing the form using the fax number or email address provided to investigators. Pregnancy should not be recorded on the Adverse Event eCRF. The investigator should discontinue study drug and counsel the patient, discussing the risks of the pregnancy and the possible effects on the fetus. Monitoring of the patient should continue until conclusion of the pregnancy. Any serious adverse events associated with the pregnancy (e.g., an event in the fetus, an event in the mother during or after the pregnancy, or a congenital anomaly/birth defect in the child) should be reported on the Adverse Event eCRF. In addition, the investigator will submit a Clinical Trial Pregnancy Reporting Form when updated information on the course and outcome of the pregnancy becomes available.

5.4.3.2 Pregnancies in Female Partners of Male Patients

Male patients will be instructed through the Informed Consent Form to immediately inform the investigator if their partner becomes pregnant during the study or within 5 months after the final dose of study drug. A paper Clinical Trial Pregnancy Reporting Form should be completed and submitted to the Sponsor or its designee immediately (i.e., no more than 24 hours after learning of the pregnancy), either by faxing or by scanning and emailing the form using the fax number or email address provided to investigators. Attempts should be made to collect and report details of the course and outcome of any pregnancy in the partner of a male patient exposed to study drug. When permitted by the site, the pregnant partner would need to sign an Authorization for Use and Disclosure of Pregnancy Health Information to allow for follow-up on her pregnancy. If the authorization has been signed, the investigator should submit a Clinical Trial Pregnancy Reporting Form when updated information on the course and outcome of the pregnancy becomes available. An investigator who is contacted by the male patient or his pregnant partner may provide information on the risks of the pregnancy and the possible effects on the fetus, to support an informed decision in cooperation with the treating physician and/or obstetrician.

5.4.3.3 Abortions

A spontaneous abortion should be classified as a serious adverse event (as the Sponsor considers abortions to be medically significant), recorded on the Adverse Event eCRF, and reported to the Sponsor immediately (i.e., no more than 24 hours after learning of the event; see Section 5.4.2).

If a therapeutic or elective abortion was performed because of an underlying maternal or embryofetal toxicity, the toxicity should be classified as a serious adverse event,

recorded on the Adverse Event eCRF, and reported to the Sponsor immediately (i.e., no more than 24 hours after learning of the event; see Section 5.4.2). A therapeutic or elective abortion performed for reasons other than an underlying maternal or embryofetal toxicity is not considered an adverse event.

All abortions should be reported as pregnancy outcomes on the paper Clinical Trial Pregnancy Reporting Form.

5.4.3.4 Congenital Anomalies/Birth Defects

Any congenital anomaly/birth defect in a child born to a female patient exposed to study drug or the female partner of a male patient exposed to study drug should be classified as a serious adverse event, recorded on the Adverse Event eCRF, and reported to the Sponsor immediately (i.e., no more than 24 hours after learning of the event; see Section 5.4.2).

5.5 FOLLOW-UP OF PATIENTS AFTER ADVERSE EVENTS

5.5.1 Investigator Follow-Up

The investigator should follow each adverse event until the event has resolved to baseline grade or better, the event is assessed as stable by the investigator, the patient is lost to follow-up, or the patient withdraws consent. Every effort should be made to follow all serious adverse events considered to be related to study drug or trial-related procedures until a final outcome can be reported.

During the study period, resolution of adverse events (with dates) should be documented on the Adverse Event eCRF and in the patient's medical record to facilitate source data verification.

All pregnancies reported during the study should be followed until pregnancy outcome.

5.5.2 Sponsor Follow-Up

For serious adverse events, adverse events of special interest, and pregnancies, the Sponsor or a designee may follow up by telephone, fax, email, and/or a monitoring visit to obtain additional case details and outcome information (e.g., from hospital discharge summaries, consultant reports, autopsy reports) in order to perform an independent medical assessment of the reported case.

5.6 ADVERSE EVENTS THAT OCCUR AFTER THE ADVERSE EVENT REPORTING PERIOD

The Sponsor should be notified if the investigator becomes aware of any serious adverse event that occurs after the end of the adverse event reporting period (defined as greater than 5 months after the final dose of study drug), if the event is believed to be related to prior study drug treatment. These events should be reported through use of the Adverse Event eCRF. However, if the EDC system is not available, the investigator should report these events directly to the Sponsor or its designee, either by faxing or by

scanning and emailing the paper Clinical Trial Serious Adverse Event/Adverse Event of Special Interest Reporting Form using the fax number or email address provided to investigators.

5.7 EXPEDITED REPORTING TO HEALTH AUTHORITIES, INVESTIGATORS, INSTITUTIONAL REVIEW BOARDS, AND ETHICS COMMITTEES

The Sponsor will promptly evaluate all serious adverse events and adverse events of special interest against cumulative product experience to identify and expeditiously communicate possible new safety findings to investigators, IRBs, ECs, and applicable health authorities based on applicable legislation.

To determine reporting requirements for single adverse event cases, the Sponsor will assess the expectedness of these events using the following reference document:

- RO7234292 Investigator's Brochure

The Sponsor will compare the severity of each event and the cumulative event frequency reported for the study with the severity and frequency reported in the applicable reference document.

Reporting requirements will also be based on the investigator's assessment of causality and seriousness, with allowance for upgrading by the Sponsor as needed.

6. STATISTICAL CONSIDERATIONS AND ANALYSIS PLAN

All patients enrolled prior to Version 4 of the protocol will not be included for any efficacy analysis. The safety data collected for these patients up to and including the end of treatment visit in Protocol BN40423 will be analyzed separately.

The primary efficacy analysis will be conducted at the end of the study (see Section 3.2). Treatment assignments will be unblinded to the Sponsor at the end of the study after the data have been cleaned and verified and the database has been locked.

Details of the planned statistical analyses mentioned below will be fully specified in a separate Statistical Analysis Plan (SAP), which will be finalized prior to the locking and unblinding of the study database.

Unless otherwise specified, all the p-values considered in Section 6 are two-sided.

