Patients who choose to enroll in the OLE will complete an end-of-treatment visit in Study BN40423, which can also serve as the inclusion visit for Study BN40955. All patients who are prematurely discontinued by the Sponsor who choose not to consent to Study BN40955 will additionally undergo a safety follow-up telephone call approximately 2 months after the last dose and a 5-month postdose safety follow-up visit.

Table 2 presents the treatment regimen for all patients before implementation of the Version 4 protocol.

[figure not shown]
**Table 2 Treatment Regimens prior to Implementation of Protocol
Version 4**

Arm	Treatment Regimen
RO7234292 Q4W arm	– RO7234292: 120 mg Q4W from Week 1 to Week 97 (25 doses)
RO7234292 Q8W arm	– RO7234292 loading dose: 120 mg at Days 1 and 29 (2 doses) – Placebo: Q8W from Week 9 to Week 97 (12 doses) – RO7234292: 120 mg Q8W from Week 13 to Week 93 (11 doses)
Placebo arm	– Placebo: Q4W from Week 1 to Week 97 (25 doses)

Q4W =every 4 weeks; Q8W =every 8 weeks.

[Figure 4](#) and [Figure 5](#) present study schema and overviews of the dosing schedule, respectively. A schedule of activities is provided in [Appendix 10](#), with additional assessments described in [Appendix 11](#), [Appendix 12](#), [Appendix 13](#), and [Appendix 14](#).

[figure not shown]
Figure 4 Study Schema for Patients Enrolled prior to Implementation of Protocol Version 4

EoT =end of treatment; HD =Huntington disease; Q4W =every 4 weeks; Q8W =every 8 weeks.

Notes: All patients who enroll prior to implementation of Protocol Version 4 will be prematurely discontinued from treatment by the Sponsor and offered treatment in the open-label extension study (BN40955). These patients will complete an EoT visit in Study BN40423, which can also serve as the screening visit for Study BN40955. All patients who are prematurely discontinued by the Sponsor who choose not to consent to Study BN40955 will additionally undergo a safety follow-up telephone call approximately 2 months after the last dose and a 5-month postdose safety follow-up visit. Patients in the Q8W arm will remain in the Q8W arm of the OLE study (BN40955). Patients in the placebo arm or Q4W arms will be randomly allocated to the Q8W or Q16W arms in Study BN40955.

Figure 5 Dosing Schema for Patients Enrolled prior to Implementation of Protocol Version 4

EoT = end of treatment; Q4W = every 4 weeks; Q8W = every 8 weeks.

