5.3.1 Adverse Event Reporting Period

Investigators will seek information on adverse events at each patient contact. All adverse events, whether reported by the patient or noted by study personnel, will be recorded in the patient's medical record and on the Adverse Event eCRF.

After informed consent has been obtained but prior to initiation of study drug, only serious adverse events caused by a protocol-mandated intervention (e.g., invasive procedures such as biopsies, discontinuation of medications) should be reported (see Section 5.4.2 for instructions for reporting serious adverse events).

After initiation of study drug, all adverse events will be reported until 5 months after the final dose of study drug or until the patient receives his or her first dose in the OLE study (BN40955), at which time reporting will occur per the new study requirements. *For patients consented to version 6 of the protocol, who have discontinued study treatment and have entered the ETT schedule of assessments, AEs will be reported until 5 months after the last dose of study drug or until the EoT for ETT Week 101 visit (whichever is longer). For patients consented to version 6 of the protocol, who have received their last dose of study treatment less than 5 months before the scheduled Week 101 EoT for ETT visit, an additional safety telephone call should be performed 5 months after the last dose.*

Instructions for reporting adverse events that occur after the adverse event reporting period are provided in Section 5.6.

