Change; PGI-S = Patient Global Impression, Severity; PK=pharmacokinetic; Q8W=every 8 weeks; RBR = Research Biosample Repository; SDMT = Symbol Digit Modalities Test; SFU = safety follow-up; SMDDS = Symptoms of Major Depressive Disorder Scale; SWR = Stroop Word Reading; TFC = Total Functional Capacity Scale; TMS = Total Motor Score; UHDRS=Unified Huntington's Disease Rating Scale.

Notes: All assessments should be performed at the scheduled visit, unless otherwise specified. On treatment days, all assessments should be performed prior to dosing, unless otherwise specified.

- ^a A maximum of one re-screening will be allowed within 8 weeks of the initial screening failure for patients who fail the initial screening (e.g., as a consequence of abnormal laboratory values or general medical status not meeting inclusion or exclusion criteria). If re-screening is required, CAG repeat length testing does not need to be repeated and the screening MRI and viral serology from the initial screening may be acceptable as part of the re-screening assessments, if performed within 12 weeks of the baseline visit.
- ^b Patients who complete the treatment period will return to the clinic for a treatment completion visit at Week 101 (i.e., the EoT visit). All patients who discontinue study treatment prematurely but do not withdraw consent for continued participation in the study will return to the clinic for study visits at Weeks 53 and 69 (if not already completed) and at Week 101 (i.e., the EoT for ETT visit) for collection of at least the data for the primary and secondary endpoints (see Sections 2.1.1, 2.1.2, and 2.2). If the ETT visit falls within \pm 30 days of either scheduled visits at Week 53 or Week 69, then only ETT will be considered. The ETT visit should be performed 28 days (\pm 3 days) after the last dose. Patients will also attend the scheduled EoT for ETT visit at Week 101 for limited assessments including the collection of the primary and secondary endpoints (see Sections 2.1.1, 2.1.2, and 2.2). Study visits should be planned as per the study schedule, however under exceptional circumstances, time window of \pm 3 days can be utilized.
- ^c Informed consent must be documented before any study-specific screening procedure is performed and may be obtained more than 28 days before initiation of study treatment.

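### The safety analysis of patients enrolled before Version 4 stops at the end-of-treatment visit, so later adverse events in patients who decline the open-label extension have no clear analysis

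*Protocol*

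**What the plan says.** **Analysis window.** Protocol Section 6 removes patients enrolled before Version 4 from all efficacy analyses and then says of their safety data: "The safety data collected for these patients up to and including the end of treatment visit in Protocol BN40423 will be analyzed separately".

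**Collection window.** Section 5.3.1 says that "all adverse events will be reported until 5 months after the final dose of study drug", or, for a patient who moves on, "until the patient receives his or her first dose in the OLE study (BN40955), at which time reporting will occur per the new study requirements". The adverse event footnote to Appendix 10, which is this cohort's own schedule, gives the same five months without the OLE exception.

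**Contacts after the end-of-treatment visit.** Under Section 3.1.1.2 the whole cohort is discontinued by the sponsor and offered the OLE. For entrants: "Patients who choose to enroll in the OLE will complete an end-of-treatment visit in Study BN40423, which can also serve as the inclusion visit" for BN40955. Patients who decline "will additionally undergo a safety follow-up telephone call approximately 2 months after the last dose and a 5-month postdose safety follow-up visit".

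**Other analysis text.** Section 6.1 restricts the safety population to patients enrolled after Version 4. Section 6.7 says the earlier patients are summarised separately in all safety analyses and gives no end date.

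**The concern.** Section 6 fixes an end date for the analysis that is earlier than the end date for collection, and it does not say what happens to the data in between. A programmer who applies the sentence as a date filter would drop an event that starts on day 60 after the last dose in a patient who declined the OLE and had the end-of-treatment visit on day 28. The protocol requires that event to be recorded and schedules two later contacts at which it could be found. Section 6.1 keeps the patient out of the main safety analysis, so the event would not appear there either.

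Within BN40423, only this cohort was randomised to Q4W dosing against placebo (Table 2, compared with Table 1). Section 5.1.2.1 reports a suspected unexpected serious reaction of ataxia in its Q4W arm. Leaving out collected post-dose events can lower the adverse event counts in its tables but cannot raise them.

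**Working it through.** The plan gives no figure on this point, so there is nothing to reproduce. The check compares the windows and sizes the difference.

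**1. Windows side by side**

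| Source | End of window for a pre-Version 4 patient |
|---|---|
| Section 6 (analysis) | End-of-treatment visit |
| Section 5.3.1 (collection) | 5 months after last dose, or first OLE dose |
| Appendix 10, adverse event footnote (collection) | 5 months after last dose |
| Section 3.1.1.2 (contacts, OLE declined) | Call at about 2 months, visit at 5 months |
| Section 6.7 (analysis) | None stated |

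Section 6 is shorter than every collection rule and does not match Section 6.7.

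**2. Share of the post-dose window after the cut-off, patient who declines the OLE**

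Inputs: 5 months = 5 × 30.44 = 152.2 days. The protocol gives no day for the sponsor-initiated end-of-treatment visit in this cohort. The nearest figure is Appendix 10, footnote b, on the early treatment termination visit: "The ETT visit should be performed 28 days", with a window of ±3 days. Using it here is an assumption.

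Share after the visit = 1 − d / 152.2, where d is the number of days from last dose to visit.

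- d = 25: 1 − 25/152.2 = 0.836
- d = 28: 1 − 28/152.2 = 0.816
- d = 31: 1 − 31/152.2 = 0.796

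The full Appendix 10 timetable gives a cross-check: last dosing visit Week 97, end of treatment Week 101, safety follow-up Week 117. The share is (117 − 101)/(117 − 97) = 16/20 = 0.80.

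The ±3 days understate the uncertainty. If the visit came 56 days after the last dose (two Q4W intervals, for illustration), the share would be 1 − 56/152.2 = 0.63.

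**3. Patient who enters the OLE**

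Reporting in BN40423 ends at the first OLE dose. The part after the cut-off is the gap from the end-of-treatment visit to that dose. Its length is not stated, and since the visit can double as the inclusion visit it may be short.

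**4. Number of patients**

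Section 5.1.1 allows the cohort size to be back-calculated: 17/0.472 = 36 on placebo, 14/0.40 = 35 on Q4W and 17/0.472 = 36 on Q8W, so 36 + 35 + 36 = 107. This is the whole cohort. The number who declined the OLE is not given, so no cohort-wide share can be computed.

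**The case against.** The strongest case on the other side has five parts.

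- **Most of the cohort may be barely affected.** All were offered the OLE, and entrants' later events are reported under BN40955. This stands. A reader might infer that most post-dose safety follow-up is dropped for all 107 patients. The documents do not support that: the 80% applies per patient and only to those who decline.
- **Section 6 does not say that later data are excluded, and Section 6.7 promises listings and summaries of all safety data.** The first half is fair as grammar. But a sentence that names an end date will be read as a cut-off, and Section 6.7 does not say it overrides it. Because Section 6 states the date itself, this is more than a detail deferred to the SAP.
- **No safety signal is lost.** Serious events in the five months are reportable within 24 hours (Sections 5.4 and 5.4.2.2) and evaluated by the sponsor (Section 5.7), and the data monitoring committee reviews safety data unblinded (Section 3.1.2). This stands. Events that began before the visit are also in the data and are followed under Section 5.5.1. What is at issue is the tabulation of events with later onset.
- **The 28-day figure belongs to a different visit.** This is correct, and it is why the share is given as an assumption with a wider illustration.
- **A common end at the end-of-treatment visit treats OLE entrants and decliners alike.** This is a reasonable motive. It is met by showing later events in their own column, which does not require leaving them unanalysed.

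**Conclusion.** The point holds in a limited form. Section 6 sets an analysis cut-off for the pre-Version 4 cohort that is earlier than the collection window in Section 5.3.1 and Appendix 10, and that does not agree with Section 6.7. Applied literally, it leaves out events that start after the end-of-treatment visit. For patients who decline the OLE this is about 80% of the post-dose window (80% to 84% with the visit at 25 to 31 days, less if the visit is later). For entrants it is only the interval to the first OLE dose.

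A reader might go further and infer that the trial's main safety comparison is weakened, or that serious late events would go unseen. Neither follows: Section 6.1 keeps this cohort outside the safety population, and the expedited reporting and committee review described above do not depend on the Section 6 sentence. The effect on incidence in this cohort has not been shown to be large, because neither the number of decliners nor the number of late events is given. Priority is minor.

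**What to change.** Replace the Section 6 sentence with wording such as:

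*All safety data collected for these patients in BN40423 up to the end of the adverse event reporting period (5 months after the final dose or the first dose in BN40955, whichever comes first) will be analyzed separately. Events with onset after the end-of-treatment visit will be shown in a separate column.*

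Add a cross-reference in Section 6.7 so that both sections use the same window, and report by arm how many patients declined the OLE.

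The cost is one sentence and a wider date filter on data already collected. The drawback is that follow-up length then differs between OLE entrants and decliners, a choice made after randomisation. The separate column makes this visible and leaves the counts up to the end-of-treatment visit available on a common footing.
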